9.5 Genital Sexually Transmitted Infection/Reproductive Tract Infection

The IoR/designee should manage STI/RTI per current CDC guidelines, available at <http://www.cdc.gov/std/treatment/>.

VR use need not be held in the event of an STI/RTI requiring treatment, unless other temporary product hold/permanent discontinuation guidelines apply. Should the IoR/designee determine that a temporary product hold is warranted, consultation with the PSRT is required.

A thorough evaluation of genital complaints is expected in the context of this study; however, syndromic management of genital symptoms is acceptable while awaiting laboratory results if such practice is in line with the local standards of care.

Investigators should use first-line oral or parenteral (in the case of syphilis or gonorrhea, for example) medications when at all possible to avoid intravaginal medication use.

9.6 Management of Specific Genital Events

If a suspected finding is reported by the participant between scheduled visits, an interim visit may be scheduled at the discretion of the site investigator. Management of genital events observed at scheduled or interim visits will be in accordance with the following:

Superficial epithelial disruption

- Continue study VR use (at study clinician's discretion)
- Perform naked eye evaluation
- Re-evaluate by speculum examination in approximately 3-5 days
- If condition worsens or does not resolve, temporarily hold study VR use and consult the PSRT; otherwise continue study VR use

Deep epithelial disruption

- Temporarily hold study product
- Re-evaluate in approximately 3-5 days and resume study VR use if resolved
- If unresolved at approximately 3-5 days, re-evaluate within approximately 2-3 days. If resolved at that time, may resume study VR use. If unresolved at this second reevaluation, continue temporary product hold, consult with PSRT regarding permanent discontinuation, and provide care per local standard
- If there is reoccurrence with no identified etiology, continue temporary product hold and consult the PSRT regarding permanent discontinuation

Localized erythema or edema: area of less than 50% of vulvar surface or combined vaginal and cervical surface

- Continue study VR use (at study clinician's discretion)
- Perform naked eye evaluation
- Re-evaluate in approximately 3-5 days
- If condition worsens or does not resolve, temporarily hold study VR use and consult the PSRT; otherwise continue study VR use

Generalized erythema or severe edema: area of more than 50% of vulvar surface or combined vaginal and cervical surface affected by erythema

- Temporarily hold study product
- Perform naked eye evaluation
- Re-evaluate in approximately 3-5 days and resume study VR use if resolved
- If unresolved at approximately 3-5 days, re-evaluate within approximately 2-3 days. If resolved at that time may resume use. If unresolved at this second reevaluation, continue temporary product hold, consult with PSRT regarding permanent discontinuation, and provide care per local standard

Unexpected genital bleeding

- Continue study VR use (at study clinician's discretion)
- Perform naked eye evaluation
- If determined to be due to deep epithelial disruption, refer to guidelines above; otherwise continue study VR use

Cervicitis (including findings on exam such as inflammation and/or friability)

- Temporarily hold study product
- Evaluate for GC/CT; consider syndromic management, pending results of testing and per clinician discretion
- If GC/CT detected, provide or prescribe treatment
- If GC/CT is not detected, re-evaluate in approximately 3-5 days. If all symptoms and signs are resolved at that time continue study VR use

Genital petechia(e)

- Continue study VR use (at study clinician's discretion)
- Perform naked eye evaluation
- No further evaluation or treatment is required

Genital ecchymosis

- Continue study VR use (at study clinician's discretion)
- Perform naked eye evaluation
- No further evaluation or treatment is required

9.7 HIV-1 Infection

Participants identified as infected with HIV will be managed or referred for management according to the local standard of care. Participants will be offered additional counseling in the clinic, if needed. If a participant has a positive test for HIV-1, study product will be permanently discontinued by the IoR/designee. Because continued study participation would be of no added benefit to participants, all follow-up visits will be discontinued and participants will be considered terminated from the study. Sites will not be responsible for paying for HIV-related care.

The level of care provided at the referral sites will be at a level that meets or exceeds the community standard for HIV-1 care. Written SOPs for referral for HIV-1 care and treatment are in place at each study site. Study site investigators have identified facilities offering psychological and social services and medical care, including antiretroviral therapy (ART), to people infected with HIV-1. Some of the research sites are part of health care institutions that provide HIV-1 care and support, and can refer women to those services. Other sites have established referral agreements with programs to expand access to ART.

Results of study laboratory testing may be helpful in clinical management; these results are provided to the participant and her medical provider as soon as they are available.

9.8 Pregnancy

In the rare event that a participant becomes pregnant during the study, the study product must be permanently discontinued.

A participant who is pregnant at the 12-Week Final Clinic Visit/Early Termination Visit will continue to be followed until the pregnancy outcome is ascertained (or, in consultation with the PSRT, it is determined that the pregnancy outcome cannot be ascertained). Pregnancy outcomes are reported on relevant CRFs; outcomes meeting criteria for EAE reporting also are reported on EAE forms.

A participant who becomes pregnant during the course of the study will have study product permanently discontinued and will be considered terminated from the study per Section 7.5.2.

A participant who becomes pregnant during the course of study participation may be offered participation in MTN-016, the HIV Prevention Agent Pregnancy Exposure Registry, if available at site. This registry study is anticipated to capture pregnancy outcomes as well as infant health information, (including growth and development), to evaluate the safety and teratogenic risks of microbicide and oral PrEP exposure in pregnancy.

For additional details about obtaining pregnancy outcome, please reference the MTN-024/IPM 031 SSP Manual (www.mtnstopshiv.org).

9.9 Criteria for Early Termination of Study Participation

Participants may voluntarily withdraw from the study for any reason at any time. The IoR also may withdraw participants from the study to protect their safety and/or if they are unwilling or unable to comply with required study procedures, after consultation with the PSRT. Participants also may be withdrawn if the study sponsor, the MTN, IPM, government or regulatory authorities, including the FDA and Office for Human Research Protections (OHRP), or site IRBs terminate the study prior to its planned end date. Every reasonable effort is made to complete a final evaluation of participants who withdraw or are withdrawn from the study prior to completing follow-up. Study staff members will record the reason(s) for all withdrawals in participants' study records.

10 STATISTICAL CONSIDERATIONS

10.1 Overview and Summary of Design

This is a multi-site, double-blinded, two arm, 3:1 randomized, placebo-controlled trial to assess the safety of dapivirine (25 mg) administered in a silicone elastomer vaginal matrix ring, when inserted once every 4 weeks during 12 weeks of study product use by healthy, sexually active, HIV-uninfected postmenopausal females, as compared with a placebo VR. A total of approximately 96 postmenopausal females (72 in the dapivirine VR arm and 24 in the placebo VR arm) will be randomized.

10.2 Study Endpoints

Primary endpoints

Consistent with the primary study objective to assess the safety of dapivirine (25 mg) administered in a silicone elastomer vaginal matrix ring, when inserted once every 4 weeks during 12 weeks of study product use by healthy, sexually active, HIV-uninfected postmenopausal females, as compared with a placebo, the primary safety endpoints are the proportion of females in each of the two arms with:

- Evidence of Grade 2 or higher genital, genitourinary and reproductive system AEs as defined by the Division of AIDS Table for Grading the Severity of Adult and Pediatric Adverse Events, Version 1.0, Dec 2004 (Clarification dated August 2009), Addendum 1, (Female Genital Grading Table for Use in Microbicide Studies) judged to be related to study product
- Evidence of Grade 3 or higher AEs as defined by the Division of AIDS Table for Grading the Severity of Adult and Pediatric Adverse Events, Version 1.0, Dec 2004 (Clarification dated August 2009)

Secondary endpoints

Consistent with the secondary study objective to evaluate acceptability of study VR expressed as women's preference for the VR compared to other HIV prevention methods in HIV-uninfected postmenopausal women, the following endpoint will be assessed:

- The proportion of participants who find the study VR to be as acceptable as other HIV prevention methods

Consistent with the secondary study objective to evaluate the adherence to the dapivirine VR versus the placebo VR for 12 weeks of continuous use, the following endpoint will be assessed:

- Adherence measures of daily study product use based on self-report for each participant over the study product use period

Consistent with the secondary study objective to evaluate the systemic and local dapivirine exposure, the following endpoint will be assessed:

- Dapivirine concentrations in plasma, vaginal fluid and cervical tissue

Exploratory Endpoints

Acceptability

- Participant's self-report on multiple components of acceptability via attitudinal questions

Adherence

- Residual amount of dapivirine measured in returned VRs
- Dapivirine concentrations in plasma, vaginal fluid, and cervical tissue

Vaginal Microenvironment

- Changes in pH, microflora and biomarkers

Note: Cervical tissue will be collected on a subset of participants taking part in the Cervical Biopsy/Vaginal Fluid Subsets

10.3 Primary Study Hypothesis

MTN-024/IPM 031 hypothesizes that a dapivirine VR will be as safe and well-tolerated as the placebo VR.

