10.4 Sample Size and Power Calculations

10.4.1 Primary Endpoints

The proposed total sample size is approximately N=96 postmenopausal females randomized to 2 arms in a 3:1 ratio giving 72 postmenopausal females in the dapivirine VR arm and 24 postmenopausal females in the placebo VR arm. The sample size is based upon the size of similar Phase 2a studies of vaginal microbicide products and includes a 3:1 ratio of drug to placebo arms to allow for the collection of additional safety endpoints in the drug arm while maintaining blinding between arms.

As a means to characterize the statistical properties of this study Table 10 presents the probability (expressed as a percent) of observing zero, at least one, and two or more safety endpoints among the 72 postmenopausal females in the dapivirine VR arm for various 'true' event rates.

Table 10: Analysis of Safety Event Frequency

Event Rate (%)	P (0 events n=72) (%)	P (≥ 1 event n=72) (%)	P (≥ 2 events n=72) (%)
0.5	69.7	30.3	5.1
1.0	48.5	51.5	16.2
3.5	7.7	92.3	72.2
5	2.5	97.5	88.1
10	0.05	99.95	99.5
15	0.0	99.99	99.99

An alternative way of describing the statistical properties of the study design is in terms of the true rate based on the observed data. Table 11 shows the exact 2-sided 95% confidence intervals for the probability of an event based on a particular observed rate. For example, if none of the 72 participants using the dapivirine VR experiences a safety event, the 95% exact 2-sided confidence interval for the true rate of event is (0.0%, 4.99%). If we see 2 events, this changes to (0.34%, 9.68%).

Table 11: Exact Two-sided 95% Confidence Intervals Based on Observing a Particular Rate of Safety Endpoints for Arms of Size 72

Observed event rate (%)	Confidence interval (%)
0.0 (0/72)	(0.0, 4.99)
1.4 (1/72)	(0.04, 7.50)
2.8 (2/72)	(0.34, 9.68)

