The primary aim of the study is to compare the safety between the two arms (dapivirine VR arm versus placebo VR arm). Assuming a two-sided Fisher's Exact test with $\alpha = .10$ and 80% or 90% power, Table 12 provides the difference in the rates of safety events (proportion of females experiencing the safety event of interest) between the dapivirine VR arm and the placebo VR arm that is detectable for a given rate in the placebo VR arm. For example, if the true rate of a given toxicity endpoint in the placebo VR arm is 4.2% (1 out of 24 females experiencing a safety event); the proposed sample size provides 90% power to detect safety endpoint rates greater than 30.2% (26.3% with 80% power).

Table 12: Difference in the Rates of Safety Events

Rate in Placebo Arm (%)	Rate in Drug Arm Detectable with 80% Power (%)	Rate in Drug Arm Detectable with 90% Power (%)
4.2 (1/24)	26.3	30.2
8.3 (2/24)	33.0	37.4
20.8 (5/24)	49.5	54.5
41.7 (10/24)	70.6	75.7
62.5 (15/24)	87.8	91.3

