10.8.2 Primary Analysis

When the use of descriptive statistics to assess group characteristics or differences is required, the following methods will be used: for categorical variables, the number and percent in each category; for continuous variables, the mean, median, standard deviation, quartiles and range (minimum, maximum). Within-treatment group assessment of the change from the baseline measurement to a follow-up measurement will be analyzed using McNemar's test (for categorical response variables) or the paired t-test or Wilcoxon signed-ranks test (for continuous variables). When use of formal testing to assess differences between users of the placebo VR and users of the dapivirine VR is required, the following methods will be used: for binomial response variables, chi-square tests and logistic regression (or exact testing methods); for continuous variables, t-tests and linear regression or nonparametric methods if data are non-Normal.

To assess the adequacy of the randomization, participants in each of the two arms will be compared for baseline characteristics including demographics and laboratory measurements using descriptive statistics.

Safety Endpoints

All females randomized into the study will be included in the primary analysis according to principle of Intent-to-Treat. To assess safety, the number and the percentages of participants experiencing each safety endpoint will be tabulated by study arm. Each participant will contribute once in each category (i.e., only for the highest severity AE for each participant) for the calculation of event rates. Exact binomial confidence intervals will be calculated for each safety endpoint for each arm and Fisher's exact test used to test for differences in event rates between the two arms.

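### The primary safety hypothesis is one of no excess over placebo, but the only between-arm safety analysis fixed is a Fisher test for a difference, with no estimate or interval for drug minus placebo

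*Protocol*

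**What the plan says.** Section 10.3 of the protocol gives the primary hypothesis: "MTN-024/IPM 031 hypothesizes that a dapivirine VR will be as safe and well-tolerated as the placebo VR". Section 10.4.1 adds: "The primary aim of the study is to compare the safety between the two arms".

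The same section sets out the planning model for that comparison: "Assuming a two-sided Fisher's Exact test with $\alpha = .10$ and 80% or 90% power", with allocation "giving 72 postmenopausal females in the dapivirine VR arm and 24 postmenopausal females in the placebo VR arm". Its worked example, for a placebo rate of 4.2%, is "90% power to detect safety endpoint rates greater than 30.2% (26.3% with 80% power".

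For the safety endpoints, section 10.8.2 plans counts and percentages by arm, and then: "Exact binomial confidence intervals will be calculated for each safety endpoint for each arm". The between-arm element is Fisher's "exact test used to test for differences in event rates between the two arms". No difference or ratio, no interval for either, no margin and no rule for reading a non-significant result is given. A general paragraph in the same section lists chi-square tests, logistic regression and exact methods for binomial variables, but names no interval and does not assign logistic regression to the safety endpoints.

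Section 10.8.3 treats adherence, a secondary endpoint, differently: the difference between the arms is to be reported with a 95% confidence interval.

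**The concern.** The hypothesis and the analysis point in opposite directions. The hypothesis is that dapivirine carries no excess risk. The test can produce evidence of a difference; when it does not, it leaves the hypothesis neither supported nor bounded. The quantity that speaks to the hypothesis is how large an excess over placebo is still compatible with the data, that is, the upper confidence limit of drug minus placebo. It is not planned.

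The exact intervals within each arm describe each rate separately. They show that the placebo rate is poorly known, but two separate intervals do not give a limit on their difference.

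At stake is the primary conclusion. With 24 women on placebo, a non-significant test is a likely result under true excesses that a safety reader would want to know about.

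**Working it through.** **Inputs.** Arms of 72 and 24; two-sided Fisher test; alpha 0.10; placebo rates 4.2% (1/24), 8.3% (2/24), 20.8% (5/24), 41.7% (10/24) and 62.5% (15/24). All are from section 10.4.1 and Table 12. The protocol states no expected placebo rate, so these rates serve as assumptions.

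**Method.** Power = sum, over all 73 × 25 possible tables (x, y) with Fisher p ≤ 0.10, of Bin(x; 72, p_drug) × Bin(y; 24, p_placebo).

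**Step 1: reproduce Table 12.** Power at the drug-arm rates that the protocol lists for 80% and 90%:

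| Placebo rate | Listed drug rates (80% / 90%) | Recomputed power |
|---|---|---|
| 4.2% | 26.3% / 30.2% | 0.803 / 0.902 |
| 8.3% | 33.0% / 37.4% | 0.798 / 0.900 |
| 20.8% | 49.5% / 54.5% | 0.798 / 0.900 |
| 41.7% | 70.6% / 75.7% | 0.801 / 0.901 |
| 62.5% | 87.8% / 91.3% | 0.799 / 0.901 |

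Table 12 is correct, so the point is not an arithmetic error.

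**Step 2: power for smaller true excesses, same test.**

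| Placebo rate | Doubling | Tripling | +10 points |
|---|---|---|---|
| 4.2% | 3% | 16% | 24% |
| 8.3% | 16% | 49% | 22% |
| 20.8% | 55% | 98% | 19% |

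On the ratio scale the answer depends strongly on the placebo rate. On the absolute scale it does not: a true excess of 10 points is missed about four times in five at each of these rates.

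**Step 3: what a non-significant result can hide.** With 1/24 on placebo, the largest drug count that stays non-significant is 14/72 (p = 0.105; 15/72 gives p = 0.065). The difference is 14/72 - 1/24 = 19.4% - 4.2% = 15.3 points.

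Newcombe 95% interval, built from the Wilson limits (l, u) of each arm:

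- drug 14/72: l = 11.95%, u = 30.03%
- placebo 1/24: l = 0.74%, u = 20.24%
- lower limit = 15.28 - √[(19.44 - 11.95)² + (20.24 - 4.17)²] = 15.28 - 17.74 = -2.5 points
- upper limit = 15.28 + √[(30.03 - 19.44)² + (4.17 - 0.74)²] = 15.28 + 11.13 = +26.4 points

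So a test result of no significant difference would sit beside an excess that could be as large as 26 points.

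**Step 4: equal observed rates.** For 3/72 versus 1/24 (both 4.2%), p = 1.0, and the Newcombe 95% interval is -16.3 to +8.1 points. Even this result leaves an excess of about 8 points open, and the planned output would not show it.

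**Step 5: what the per-arm intervals offer.** For 1/24 the exact 95% interval is 0.1% to 21.1%. It signals imprecision on placebo but puts no limit on the excess.

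**The case against.** The strongest reply is that the limited sensitivity is disclosed. Table 12 and its example say openly that, against 4.2% on placebo, only drug rates of about 26% or 30% are detectable. Section 10.4.1 also says that the size follows similar Phase 2a studies and that 3:1 allocation is meant to gather safety data in the drug arm. Section 2.8.1 states the hypothesis without a comparator. Exact intervals by arm are planned, so a p-value will not stand alone, and the risk difference can be computed from the planned counts. Interval methods are often left to a statistical analysis plan, which is not shown here.

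Much of this stands, and it lowers the severity. It does not remove the mismatch: the protocol itself fixes the comparative hypothesis in 10.3 and the between-arm method in 10.8.2, and it specifies a difference with an interval for a secondary endpoint but not for the primary one. Disclosing low power at the design stage does not supply the bound at the analysis stage.

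Four stronger readings are tempting, and the document does not support them.

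- A reader might infer that the sponsor will report non-significance as proof of equal safety. No section says so, and no decision rule is given. The risk comes from pairing 10.3 with 10.8.2.
- A reader might infer that the test misses any several-fold excess. That holds only at low placebo rates: a tripling has 49% power at 8.3% and 98% at 20.8%.
- A reader might infer that alpha 0.10 conflicts with 95% intervals in the primary analysis. The only alpha stated for this test is 0.10, and 10.8.2 gives no level for its per-arm intervals.
- A reader might conclude that a formal non-inferiority design is needed. A Phase 2a study framed as estimation does not require one.

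**Conclusion.** The point holds as a mismatch between the primary hypothesis and the analysis fixed for it. The Fisher test can refute the claim of no excess but cannot support it, and nothing planned bounds the excess over placebo. If the placebo rate is 4.2%, 8.3% or 20.8%, power is 3%, 16% or 55% for a doubling and about 19% to 24% for a 10-point excess. An observed excess of 15 points (14/72 versus 1/24) can be non-significant with an upper 95% limit of +26.4 points. These figures assume full arms of 72 and 24, two-sided alpha 0.10, and placebo rates borrowed from Table 12 because the protocol gives none. The power statements in the protocol are themselves correct, and they already disclose the low sensitivity. It should be fixed, but it does not invalidate the design.

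**What to change.** In section 10.8.2, add for each of the two primary safety endpoints the drug-minus-placebo risk difference with a confidence interval, reported alongside the Fisher test. Newcombe, Miettinen-Nurminen or exact unconditional intervals would all serve; name one. Use 90% to match the alpha of 0.10 in section 10.4.1, or 95% as already planned for adherence in 10.8.3.

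Reword section 10.3 so that the aim is to estimate the excess risk over placebo. State that the conclusion rests on the upper limit of the interval, and that a non-significant p-value is not evidence of equal safety.

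The cost is one table column, a few sentences and a conclusion that will sound less favourable. No participants, visits or data are added.

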10.4 Sample Size and Power Calculations

10.4.1 Primary Endpoints

The proposed total sample size is approximately N=96 postmenopausal females randomized to 2 arms in a 3:1 ratio giving 72 postmenopausal females in the dapivirine VR arm and 24 postmenopausal females in the placebo VR arm. The sample size is based upon the size of similar Phase 2a studies of vaginal microbicide products and includes a 3:1 ratio of drug to placebo arms to allow for the collection of additional safety endpoints in the drug arm while maintaining blinding between arms.

As a means to characterize the statistical properties of this study Table 10 presents the probability (expressed as a percent) of observing zero, at least one, and two or more safety endpoints among the 72 postmenopausal females in the dapivirine VR arm for various 'true' event rates.

Table 10: Analysis of Safety Event Frequency

Event Rate (%)	P (0 events n=72) (%)	P (≥ 1 event n=72) (%)	P (≥ 2 events n=72) (%)
0.5	69.7	30.3	5.1
1.0	48.5	51.5	16.2
3.5	7.7	92.3	72.2
5	2.5	97.5	88.1
10	0.05	99.95	99.5
15	0.0	99.99	99.99

An alternative way of describing the statistical properties of the study design is in terms of the true rate based on the observed data. Table 11 shows the exact 2-sided 95% confidence intervals for the probability of an event based on a particular observed rate. For example, if none of the 72 participants using the dapivirine VR experiences a safety event, the 95% exact 2-sided confidence interval for the true rate of event is (0.0%, 4.99%). If we see 2 events, this changes to (0.34%, 9.68%).

Table 11: Exact Two-sided 95% Confidence Intervals Based on Observing a Particular Rate of Safety Endpoints for Arms of Size 72

Observed event rate (%)	Confidence interval (%)
0.0 (0/72)	(0.0, 4.99)
1.4 (1/72)	(0.04, 7.50)
2.8 (2/72)	(0.34, 9.68)

The primary aim of the study is to compare the safety between the two arms (dapivirine VR arm versus placebo VR arm). Assuming a two-sided Fisher's Exact test with $\alpha = .10$ and 80% or 90% power, Table 12 provides the difference in the rates of safety events (proportion of females experiencing the safety event of interest) between the dapivirine VR arm and the placebo VR arm that is detectable for a given rate in the placebo VR arm. For example, if the true rate of a given toxicity endpoint in the placebo VR arm is 4.2% (1 out of 24 females experiencing a safety event); the proposed sample size provides 90% power to detect safety endpoint rates greater than 30.2% (26.3% with 80% power).

Table 12: Difference in the Rates of Safety Events

Rate in Placebo Arm (%)	Rate in Drug Arm Detectable with 80% Power (%)	Rate in Drug Arm Detectable with 90% Power (%)
4.2 (1/24)	26.3	30.2
8.3 (2/24)	33.0	37.4
20.8 (5/24)	49.5	54.5
41.7 (10/24)	70.6	75.7
62.5 (15/24)	87.8	91.3

